We will use a three group randomized design in 150 older (60-85 years), obese (BMI=30-40 kg/m² or BMI= 27.0-<30 kg/m² plus one risk factor), men and women who will undergo a 12 month WL intervention to test our overall hypothesis that weighted vest use added to WL will better preserve bone health compared to WL alone and similarly to WL plus a structured RT intervention. All groups will receive the same WL intervention (caloric restriction targeting 10% WL and with adequate calcium, vitamin D, and protein intake), in accordance with national obesity treatment guidelines.⁶⁵ Thus, treatment groups are: WL alone (**WL**; n=50); WL plus weighted vest use (**WL+VEST**; targeting 8 hours/d, weight replacement titrated up to 10% WL; n=50); or, WL plus structured RT (**WL+RT**; targeting 3 sessions/week; n=50); **Table 1.** All outcome assessments occur at baseline, six, and 12 months.

Table 1. Proposed Intervention Components by Treatment Group.

Intervention Components	Intensive WL Phase (Months 1-6)	Reduced Contact WL Phase (Months 7-12)
Weight Loss (WL)	Weekly behavioral-based group sessions; 10% WL goal following national obesity treatment guidelines	Biweekly behavioral-based group sessions; 10% WL goal following national obesity treatment guidelines
WL + Weighted Vest (WL+VEST)	WL + 8 hours/day weighted vest use titrated weekly to adjust for achieved WL (up to 10% baseline weight)	WL + 8 hours/day weighted vest use titrated biweekly to adjust for achieved WL (up to 10% baseline weight)
WL + Resistance Training (WL+RT)	WL + 3 days/week progressive, structured RT	

Recruitment of study participants: Randomization of 150 participants will ensure at least 85% statistical power (with a conservative drop-out rate of ~15%; n=128 completed) to detect significance between group differences in our primary outcome (12 month total hip trabecular vBMD). We plan to recruit, screen and enroll during Years 1-3.5 of the study. We will target older adults who live in the area via media advertisements and mass mailings.

Participant screening and randomization

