established at $p<0.025$. Next, the noninferiority of WL+VEST compared to WL+RT will be determined based on whether the lower bound of the one-sided confidence interval for the estimated 12 month treatment effect of WL+VEST versus WL+RT overlaps the -4.0% non-inferiority boundary for total hip trabecular vBMD. This will be performed using $\alpha=0.0125$ to account for co-primary hypotheses as well as for using a 1-sided alternative hypothesis. Tests for both co-primary hypotheses will be based on different contrast statements from the same statistical model. Secondarily, we will repeat these analyses with the short-term effect at 6 months of both interventions as an exploratory analysis. For Aim 2, we will repeat these analyses for the 12 month effect (and secondarily 6 month effect) using total hip aBMD assessed by DXA as the outcome. Comparisons will be performed for both superiority of WL+VEST vs. WL as well as noninferiority of WL+VEST vs WL+RT based on a 2.13% noninferiority margin using the methods described above. Analytic models for all other Aim 2 outcomes will mirror the model used in the primary aim, with the important exception that comparisons will focus on statistical comparisons of group mean differences. All outcomes are assessed at 6 and 12 months, and while both visit time points will be estimated, the 12 month treatment effect will be considered of primary interest. Treatment effects for changes in outcome variables are compared using a mixed model fit with treatment group, visit, and treatment by visit interaction, adjusted for sex and baseline values of the outcome. Tests will be performed using contrast statements at 12 months (primarily) and 6 months (secondarily), and we will use the partial F-test $p<0.05$ for significance. Significant comparisons for secondary outcomes will further use comparisons of all three groups at each visit using $p<0.0167$ for pairwise significance. Lastly, we intend to explore the associations between 6 and 12 month change in vBMD or aBMD with change in secondary outcome measures (i.e., DXA and CT-acquired body composition, D3Cr muscle mass, biomarkers of bone turnover, bone regulating hormones/cytokines) using linear regression methods and adjusted for sex and treatment group, to explore potential mechanisms underlying the treatment effect. Secondary comparisons will not be adjusted for multiplicity other than for pairwise group comparisons. Statistical analyses will be conducted using SAS v9.4 (SAS Institute, Cary, NC) and R software.

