To evaluate limb loading, an analysis of covariance (ANCOVA) to test for mean differences between groups in daily loading metrics (cumulative loading, peak force, loading rate, impulse). To evaluate femoral stress and strain, an ANCOVA will also be used with femoral mechanical stress and strain as the dependent variable. In the event of significant differences, post-hoc independent two-sample t-tests using a Bonferroni adjusted alpha = 0.025 will further be tested. Fifteen participants per group provides 80% power to detect a moderate effect size (Variance between/Variance within) of 0.40 using a 0.05 Type I error rate and 87% retention at 6 months. Cohen's *d* effect sizes will be calculated to further contextualize group differences and inform future sample size calculations. Pearson product moment will also explore associations between daily limb loading metrics, change in areal and volumetric BMD, and changes in physical function separately by group and across all groups combined.

Human Subjects Protection

Subject Recruitment Methods: We will recruit individuals using community-based recruitment strategies including newspaper ads and mass mailings. We will also advertise in the Sticht Center recruitment newsletter (Volunteers in Touch with an Active Lifestyle: VITAL), utilize WakeOne recruitment letters, and participate in community outreach events.

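### Limb-loading sub-study: the pairwise t-tests leave the ANCOVA that triggers them, the compared pairs are not named, and a large detectable effect is called moderate

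*Combined protocol and SAP*

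**What the plan says.** The section on statistical analysis and power for the Limb Loading Sub-Study plans "an analysis of covariance (ANCOVA) to test for mean differences between groups in daily loading metrics", and a second ANCOVA for femoral stress and strain. It names no covariates. The pairwise step is run only if the ANCOVA is significant: "post-hoc independent two-sample t-tests using a Bonferroni adjusted alpha = 0.025 will further be tested". The section does not say how many groups or which pairs are compared.

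On size it states: "Fifteen participants per group provides 80% power to detect a moderate effect size (Variance between/Variance within) of 0.40". The calculation takes an omnibus alpha of 0.05 and assumes that 87% are retained at six months.

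The parent trial works differently. Its Statistical Analysis Plan paragraph takes both co-primary tests as contrasts from one mixed model. For other Aim 2 outcomes it uses a partial F-test at 0.05, then "comparisons of all three groups at each visit using $p<0.0167$ for pairwise significance". The power paragraph for all other Aim 2 outcomes describes a variance ratio of 0.116 as relatively modest.

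**The concern.** An ANCOVA compares adjusted means and estimates residual variance from all arms together. An independent two-sample t-test compares raw means and estimates variance from two arms only. If the first is the gate and the second is the follow-up, they answer different questions. The ANCOVA can be significant while no t-test is, or a t-test can reflect a covariate imbalance that the ANCOVA removed. With about 13 completers per arm, any precision given up is noticeable.

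Two smaller matters sit in the same paragraph. The alpha cannot be checked against the comparisons because these are not listed. And describing the detectable effect as moderate invites a reader to take a null result as evidence against moderate effects, in a pilot whose effect sizes are meant to inform later sample-size calculations.

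**Working it through.** **Inputs.** From the sub-study section: 15 per group, 87% retention, variance ratio 0.40, omnibus alpha 0.05, post-hoc alpha 0.025. Completers: 15 × 0.87 = 13.05, so n = 13 per arm. Number of groups: k = 3, taken from the parent design ("We will use a three group randomized design in 150 older") because the sub-study section does not state it.

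**1. The stated 80% power.** One-way ANOVA with a noncentral F, between-group variance using divisor k − 1:
- λ = (k − 1) × n × 0.40 = 2 × 13 × 0.40 = 10.4, with df 2 and 36.
- Power = 79.7% (79.8% at n = 13.05), so the 80% reproduces.
- Other readings do not reproduce it: divisor k gives 93.4%, 0.40 read as Cohen's f gives 56.4%, and k = 2 with divisor k − 1 gives 59.0%.
- The same divisor returns 80.0% for the parent trial's ratio of 0.116 at 50 × 0.85 = 42.5 per group. This supports both the convention and k = 3.

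**2. What a ratio of 0.40 means.**
- f = √(0.40 × 2/3) = 0.516.
- If one arm differs from two equal arms: d = √(3 × 0.40) = 1.10 SD.
- If two arms are at the extremes and the third is midway: d = √(4 × 0.40) = 1.26 SD.
- Against the parent trial's ratio: 0.40 / 0.116 = 3.4 times as large.
- At f = 0.25 (the conventional medium value, an assumption not in the documents), λ = 39 × 0.0625 = 2.44 and power is 25%.

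**3. t-test versus model contrast.** Two-sided alpha 0.025, d = 1.1, n = 13 per arm, noncentrality d × √(n/2) = 1.1 × √6.5 = 2.80:

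| Pairwise test | df | Noncentrality | Power |
|---|---|---|---|
| Two-sample t-test | 24 | 2.80 | 66% |
| Contrast, pooled error only | 36 | 2.80 | 68% |
| Contrast, one covariate with R² = 0.20 (assumed) | 35 | 2.80/√0.8 = 3.14 | 78% |

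Pooling alone is worth about 2 percentage points. The rest depends on a covariate effect that the documents do not give.

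**4. The alpha.**
- 0.05/2 = 0.025, which is Bonferroni for two comparisons. 0.05/3 = 0.0167, which is Bonferroni for three and is the parent trial's pairwise value.
- Simulated family-wise error under the global null (400,000 runs, 13 per arm, t-tests at 0.025):

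| Pairs tested | With the omnibus gate | Without the gate |
|---|---|---|
| Three | 4.5% | 6.4% |
| Two | 3.4% | 4.6% |

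- If one of three arms truly differs, only one pair remains truly null, and it is tested at 0.025. The gated procedure is therefore below 5% in that case too.
- Moving the t-tests from 0.025 to 0.0167 lowers power from 66% to 59% at d = 1.10, and from 79% to 74% at d = 1.26.

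**The case against.** The strongest defence is that this is a pilot with a feasibility component, that no parent-trial conclusion depends on it, and that Cohen's d will be reported beside the tests. All of that stands and keeps the severity low.

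A reader might infer that 0.025 matches no valid correction for three groups, or that error is inflated. The documents do not support either. 0.025 is exactly the two-comparison Bonferroni value, and the Specific Aims are built on two comparisons involving WL+VEST. The 6.4% figure belongs to an ungated procedure, whereas the plan makes the t-tests conditional on the ANCOVA. The t-tests are also not unadjusted for multiplicity; what they lack is covariate adjustment. What remains is that the pairs are not named.

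It is also fair to say that the precision gain is mostly hypothetical. No covariates are named, and without them the gain is 66% to 68%. Pooling error also assumes equal variances across arms that are loaded differently; a two-arm t-test does not borrow variance from the third arm. This is a real cost of the contrast, but the ANCOVA gate already makes the same assumption.

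Finally, a reader might take the 25% power at f = 0.25 to show that the 80% is wrong. It does not. The plan gives the value 0.40 with its scale and never claims 80% power at f = 0.25. Only the adjective is at fault.

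**Conclusion.** The point holds as a low-severity matter of analysis choice and wording.

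- **Pairwise method.** The t-tests drop the covariates and pooled error of the ANCOVA that triggers them, so they can disagree with it. The demonstrable loss is about 2 percentage points of power (66% against 68% at 1.1 SD, 13 per arm, alpha 0.025). It rises to about 12 points only if covariates explain an assumed 20% of variance.
- **Alpha.** There is no inflation with the gate in place. The gap is that the plan does not say which comparisons the 0.025 covers.
- **Effect label.** The 80% is correct. A ratio of 0.40 (f about 0.52, arm differences of about 1.1 to 1.3 SD) is large, and is 3.4 times what the same document calls relatively modest.

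These figures assume three groups in the sub-study, 13 completers per arm, normal outcomes with equal variances, and the k − 1 divisor that reproduces the plan's own power.

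**What to change.** In the sub-study's statistical section:

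1. Replace the two-sample t-tests with pairwise contrasts of adjusted means from the same ANCOVA, still conditional on a significant omnibus test. This is the parent trial's own practice of taking contrasts from the fitted model.
2. State the number of groups, the ANCOVA covariates and the pairs to be compared. Match the alpha to the pairs: 0.025 if they are WL+VEST against each of the other two arms, or 0.0167 if all three pairs are tested, as in the parent trial. Either is defensible.
3. Check residual variances by arm, since the contrast pools them.
4. Describe 0.40 as a large effect, giving f of about 0.52 and arm differences of about 1.1 to 1.3 SD. Leave the 80% as it is.

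The cost is a few sentences in the plan. Data, visits, sample size and software do not change.

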In addition to receiving dietary counseling, all participants will be asked to attend virtual or in-person behavioral counseling group sessions led by the RD. These sessions will be held weekly for the first 6 months and bi-weekly for the remainder of the study to provide participants an opportunity to review specific questions and problems. The education and counseling component of the intervention will emphasize instruction in making healthy, lower-calorie food choices while teaching changes in behavioral habits to promote WL and prevent weight regain.⁷³ Specific emphasis will be placed on the acquisition and use of self-management skills, particularly self-monitoring of diet and weight, and achieving 150 minutes of aerobic activity/week, in accordance with national guidelines.^{65,74} Throughout the 12 month WL phase, participants will be asked to track their food/beverage intake (including the number of meal replacements consumed each day) daily for the first three months and then on a reduced schedule as warranted. These will be reviewed routinely by the study registered dietitian. Body weight will be measured and recorded at all group sessions to provide additional feedback and to increase motivation. Official study weights will occur at SV3, FV2, and FV4. If it is evident (either through review of diet records or inadequate WL) that participants are struggling to meet their WL goals additional individual counseling sessions with the RD will be held to improve compliance. At FV1 and FV3, participants in this group will be asked to complete a program evaluation form to solicit feedback on overall WL program satisfaction, desired future usage, and product preferences. Periodically throughout intervention, participants will be asked to rate their confidence (i.e., self-efficacy) in meeting the demands of the intervention they are receiving. They will also be asked to report changes in their health and medication.

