Phone Screener	x											
Informed consent/HIPAA		x										
Demographics		x										
Medical history		x	x									
Medications		x	x	x	x		x	x		x	x	x
Depression (CES-D)		x	x				x			x		x
Cognitive Assessment (MoCA)		x								x		
Pittsburgh Fatigability Scale					x		x			x		x
PROMIS Pain Intensity and Fatigue					x		x			x		x
CHAMPS physical activity		x	x				x			x		x
Adverse Events				x	x	x	x	x	x	x	x	x
Physical Exams and Physical Performance Measures												
Vital signs (ht/wt/bp/pulse)		x		x	x		x	x		x	x	
Anthropometric Measures				x			x			x		
eSPPB				x			x			x		
Hand Grip Test				x			x			x		
RMR					x			x			x	
Activity Monitor - thigh				x			x			x		
Activity Monitor - in vest						x			x			
400 meter Walk – fast				x			x			x		
TUG				x			x			x		
Biodex					x				x		x	
Stair climb				x			x			x		
Radiology/Imaging Tests												
DXA (whole body, hip, spine, forearm)				x			x			x		
CT (hip and spine)					x			x			x	
Phlebotomy												
CBC		x										
Metabolic Panel		x										
Vitamin D					x							
Plasma/Serum Storage					x				x		x	
Other												
D3-Creatine muscle mass (dose/collection)				x	x					x	x	
Run-in instructions		x		x								
Participant Satisfaction									x			x
Self-Efficacy						x			x			x
Adherence monitoring (weight, dietary trackers, meet with study dietitian as needed)						x			x			

Table 3. Proposed Assessment Timeline.

PS=phone screen, SV=screening visit, FV=follow up visit, INT=intervention; eSPPB =expanded short physical performance battery, RMR=resting metabolic rate, TUG=timed up and go, DXA=dual energy x-ray absorptiometry, CT=computed tomography, CBC=complete blood count.

Study Measure(s)

Methods for Primary Outcome Measure Assessment. Our study is powered to detect group differences in our primary outcome of 12 month change in total hip trabecular vBMD measured from CT scans acquired at baseline and 12-month follow-up visits. CT scans will also be acquired at a 6-month visit to assess changes in the outcomes at the end of the intensive WL phase. For completeness, below we describe the CT scanning protocol and vBMD image acquisition and assessment methods for the total hip, femoral neck, and lumbar spine regions of interest.

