calculated using the Weir equation. Accelerometry will be used to objectively assess physical activity over a seven day period at baseline, 6 and 12 months using a triaxial accelerometer and inclinometer.¹⁰⁵ Finally, questionnaires assessing fatigue/fatigability¹⁰⁶, pain¹⁰⁷, physical activity¹⁰⁸, and intervention adherence self-efficacy (with questionnaire specific to INVEST modeled on prior work¹⁰⁹) will be assessed. If covariates are found to be unbalanced between groups, and related to study outcomes, these variables will be included as covariates in exploratory, secondary statistical analyses. Lastly, adverse events will be assessed and recorded by asking participants to complete a bi-monthly health status questionnaire. Spontaneously reported adverse events will also be collected and reported by study staff.

Data and Statistical Analyses

Data Management. Data will be collected on forms at the clinic site and transferred to a secure electronic database. Our web-based management system will assure integrity and validity. Dynamic reports and statistical analyses will monitor quality. A participant-based inventory system will track recruitment, retention, adherence, and missing data from entry through exit, close-out, and lock-down of final datasets.

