- 3) The risks of intervention-related problems with wearing the weighted vests may include: 1) an increased fall risk and 2) an exacerbation of prior conditions related to knee/back/shoulder pain. We exclude potential participants who report knee/back/shoulder pain with prescription medication use during the initial phone screen. Participants will also be advised to not wear the weighted vest during strenuous activities. Additionally, at the outset of all group sessions, participants will be queried regarding problems or health symptoms they may be experiencing with the vest. The interventionist will record the presence or absence of such symptoms and determine whether or not the contact should be handled emergently or, in consultation with the study physician, by a scheduled appointment with the primary care provider.
- 4) The risks of the structured resistance exercise intervention may include: 1) musculoskeletal complications and muscle soreness in the early phases of the intervention, and 2), an increased fall risk. These risks are minimized since all center-based exercise sessions will be supervised by trained exercise technicians who will instruct participants in proper balance safety and footwear to use. Procedures to minimize musculoskeletal and cardiac injury and muscle soreness include warm-up and cool-down activities that include large muscle movements and stretching. Participants will begin with an easier exercise stimulus and will gradually increase in intensity over the first few months. Exercise physiologists, trained in cardiac life support, will supervise all center-based exercise sessions and practice codes are conducted quarterly.

Assessment risks: Health risks for each of the assessment procedures may include:

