Safety measures during the interventions: For the dietary intervention, all study participants are monitored for compliance to a safe level of caloric deficit. Since the degree of bone and muscle loss is accelerated by the rate of weight loss, all participants will be weighed weekly and if weight is being lost at a rate greater than 0.9 kg/wk (~2 lb/wk), adjustments may be made to the meal plan to increase the level of calories recommended to slow down this excess rate of weight loss. As stated previously, at the outset of all group sessions, participants will be queried regarding problems or health symptoms they may be experiencing with the vest. The interventionist will record the presence or absence of such symptoms and determine whether or not the problem requires medical attention and, if so, to determine whether or not the contact should be handled emergently or, in consultation with the study physician, by a scheduled appointment with the primary care provider. Supervised RT sessions are conducted at a central location and are supervised by trained interventionists who monitor potential adverse experiences and symptoms. On-site staff trained in advanced cardiac life support are available to deal with medical emergencies. Also, institutional and community EMS services will be activated if needed. Procedures to minimize musculoskeletal discomfort to the exercise include teaching proper warm-up and cool down activities and providing instruction on correct exercise techniques and fall safety. If for any reason the participant reports a fall or other injury, or chest pain, shortness of breath, or dizziness, during a supervised RT session, they will be referred to their doctor, or study staff will notify the participant's doctor or other health care provider with their permission. If at any point during a RT session, participants develop chest pain, shortness of breath, or dizziness, they will be instructed to stop exercise, and to contact the study staff if these symptoms persist or recur. We monitor blood pressure and heart rate before and after all supervised RT sessions. If an intervention-related injury or illness does occur, the study medical staff will be consulted according to the type of symptom reported. In some instances, it may be appropriate to reduce or to temporarily suspend the participant's weight loss, vest use, or RT goals. If the injury or symptoms do not resolve after an appropriate period of time, the participant will be referred to his/her primary care provider for further evaluation. The participant will be encouraged to follow the primary care provider's instructions regarding intervention compliance.

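### The only symptom question described for the start of group sessions is about the vest, so non-serious events could be recorded more often in WL+VEST than in WL if arm-specific sources are combined with the common ones

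*Combined protocol and SAP*

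**What the plan says.** **Query at group sessions.** Potential Risks (Intervention risks, item 3) and Safety measures during the interventions both describe the same step at the start of every group session: "participants will be queried regarding problems or health symptoms they may be experiencing with the vest". The second section continues: "The interventionist will record the presence or absence of such symptoms and determine whether or not the problem requires medical attention". No other symptom question is described for the start of a session. On frequency, the Weight Loss Intervention section, which applies to all groups, says: "These sessions will be held weekly for the first 6 months and bi-weekly for the remainder of the study".

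**Other arm-specific sources.** The WL+VEST section adds a daily participant log that includes complications of vest use, which staff go over at group sessions. For WL+RT, Safety measures during the interventions says that staff at supervised sessions watch for adverse experiences and symptoms.

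**Sources common to all arms.** Descriptive Data, Potential Covariates, and Adverse Events gives the formal route: "adverse events will be assessed and recorded by asking participants to complete a bi-monthly health status questionnaire". It adds: "Spontaneously reported adverse events will also be collected and reported by study staff". The Weight Loss Intervention section says of participants: "They will also be asked to report changes in their health and medication". In Table 3 the row "Adverse Events" is marked at SV2, SV3, both intervention periods, FV1 to FV4 and the phone column, with no distinction by arm.

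**Analysis.** Statistical Analyses provides for regular monitoring of serious adverse events for the DSMB. It specifies no between-arm comparison of adverse events. Nothing says whether vest-query, vest-log or training-session findings enter the adverse-event data.

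**The concern.** The vest risks that the protocol names are falls and worsening of knee, back or shoulder pain. Neither is peculiar to vest wearers: fall prevention is discussed with all participants, and fall risk is also listed for resistance training. How many such events are recorded depends on how often, and how directly, people are asked.

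WL is the natural comparator for vest safety, and on the plan as written it is the least-observed arm. If the extra findings from WL+VEST and WL+RT are added to the common adverse-event data, WL could look safer than the other two arms when true rates are equal. The background section presents the vest as a more available and cheaper alternative to resistance training, so its tolerability is part of the case for it. If the source of an event is not recorded at the time, it cannot be reliably reconstructed later.

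**Working it through.** The plan states no figure on this point, so there is none to reproduce. The check has three steps.

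**1. Solicited contacts over 12 months, per participant**

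- Vest queries, from the Table 3 weeks: 24 weekly sessions (weeks 1-24) + 28/2 = 14 biweekly sessions (weeks 25-52) = 38. Counting by half-years instead gives 26 + 13 = 39.
- Common questionnaire: 12/2 = 6 if bi-monthly means every two months, or 12 × 2 = 24 if it means twice a month. The protocol does not define it.
- Supervised RT sessions: up to 3 × 52 = 156.

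**2. Sources by arm, as described**

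| Source | WL | WL+VEST | WL+RT |
|---|---|---|---|
| Bi-monthly questionnaire | yes | yes | yes |
| Spontaneous reports | yes | yes | yes |
| Periodic request for health changes | yes | yes | yes |
| Table 3 adverse-event assessments | yes | yes | yes |
| Symptom query at session start | none described | vest query, about 38 | none described |
| Daily complications log | no | yes | no |
| Symptom monitoring at training | no | no | up to 156 sessions |

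The imbalance lies wholly in the last three rows. Spontaneous reports are common to all arms in form, but WL+RT participants have many more staff contacts at which to make them.

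**3. Illustration of what combining sources could do**

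The true risks and detection rates here are assumptions; none comes from the documents. Let the true 12-month risk p be equal in WL and WL+VEST, with detection d0 in WL and d1 in WL+VEST. The recorded risks are p0 = p × d0 and p1 = p × d1, so the recorded ratio is d1/d0. With n = 50 per arm (no attrition), the chance of a nominally significant excess in WL+VEST at two-sided 0.05 is

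Φ{ [(p1 − p0) − 1.96 √(2 p̄(1 − p̄)/n)] / √[p0(1 − p0)/n + p1(1 − p1)/n] }, with p̄ = (p0 + p1)/2.

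| p | d0, d1 | Recorded WL vs WL+VEST | Difference (points) | Ratio | Chance of false excess |
|---|---|---|---|---|---|
| 20% | 90%, 95% | 18% vs 19% | 1 | 1.06 | 3.4% |
| 20% | 70%, 90% | 14% vs 18% | 4 | 1.29 | 7.8% |
| 20% | 50%, 90% | 10% vs 18% | 8 | 1.80 | 20.8% |
| 40% | 90%, 95% | 36% vs 38% | 2 | 1.06 | 4.0% |
| 40% | 70%, 90% | 28% vs 36% | 8 | 1.29 | 13.4% |
| 40% | 50%, 90% | 20% vs 36% | 16 | 1.80 | 42.8% |

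With equal detection, the one-direction rate would be about 2.5% (half of 0.05). The result therefore runs from negligible to large, depending on how complete the common questionnaire is. The illustration also supposes that a question about the vest raises detection of the event in question. That is plausible for shoulder or back pain during wear, and less clear for symptoms that a participant does not link to the vest.

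**The case against.** The strongest reply is that the formal adverse-event route is already the same in every arm. The questionnaire and spontaneous reports carry no restriction by arm, all groups are asked about health changes, and Table 3 makes no distinction. Pain, one of the named vest risks, is also measured by the PROMIS instrument at SV3, FV1 and FV3 in all arms. The vest query is described as triage, to decide whether and how a problem needs medical attention, and extra checks for a device-specific hazard are ordinary participant protection. The planned safety monitoring concerns serious events, which depend less on prompting.

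Most of this stands, and it rules out several stronger readings that a reader might infer:

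- *That WL has only the questionnaire and spontaneous reports.* The health-change request and the Table 3 assessments also apply to WL.
- *That events from all sources are pooled.* The documents do not say so.
- *That safety cannot be compared fairly between arms.* The common questionnaire allows a like-for-like comparison if it is analysed separately.
- *That the vest will look 1.3 to 1.8 times less safe.* That ratio only divides one assumed detection rate by another, and the high-detection scenario gives 1.06.

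The reply does not settle whether the arm-specific findings count as adverse events. Table 3 marks adverse events during both intervention periods, exactly when the vest queries and training sessions take place, and no source field or counting rule is described.

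**Conclusion.** The point holds as a modest weakness in how adverse events are ascertained. The session-start query, the vest log and the training-session monitoring give WL+VEST and WL+RT opportunities for detection that WL lacks. If these sources are combined with the common ones, non-serious events could be recorded more often in those two arms at equal true rates. Whether they will be combined is not stated.

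The contact counts (about 38 vest queries against none in WL) follow from the schedule. The size of any bias does not follow from the documents: the illustrated 3% to 43% chance of a false excess rests entirely on assumed risks and detection rates. The text supports a risk of unequal detection, not an established bias, and no planned between-arm adverse-event test is invalidated because none is specified. The primary vBMD analysis is unaffected. This is an inexpensive improvement rather than the correction of an error.

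**What to change.** 1. Keep the vest query as it is. Before it, ask every participant in all three arms the same neutral question about symptoms, falls and injuries at the start of each group session. Putting the neutral question first keeps the vest query from prompting the answer.
2. Add a field to the adverse-event form for the source of each event: questionnaire, neutral question, spontaneous report, vest query, vest log or training session.
3. State that any between-arm adverse-event summary uses the common sources only (questionnaire and neutral question), and list vest-query, vest-log and RT-session findings separately. Define bi-monthly in the same place.

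The cost is a minute or two at sessions that already take place, one form field and a few sentences in the plan. No existing monitoring is reduced. Equal questioning will not remove differences in reporting that arise because participants know their arm.
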